10.0 CRITERIA FOR EVALUATION AND ENDPOINT DEFINITIONS

- 10.1 Overall Survival: Measured from date of randomization to date of death from any cause. Patient known to be alive are censored at date of last contact.
- 10.2 Disease-Free Survival: Measured from date of randomization to date of first observation of recurrence or death due to any cause. Patients without recurrence are censored at date of last contact.
- 10.3 **Performance Status:** Patients will be graded according to the current Southwest Oncology Group grading scale:
- | GRADE | SCALE |
|---------------------|---|
| 0 | Fully active; able to carry on all predisease activities without restriction. |
| 1 | Restricted in physically strenuous activity but ambulatory and able to carry out work of a light or sedentary nature, e.g., light housework, office work. |
| 2 | Ambulatory and capable of all self-care but unable to carry out any work activities. Up and about more than 50% of waking hours. |
| 3 | Capable of only limited self-care; confined to bed or chair more than 50% of waking hours. |
| 4 | Completely disabled. Cannot carry on any self-care. Totally confined to bed or chair. |
| 5 | Dead |
- 10.4 PSA Progression: A serum PSA level of > 0.2 ng/mL measured on 3 consecutive occasions or in the absence of increasing PSA, a positive bone scan result or other radiographic or histologic evidence of progression will be used. Date of progression will be the date that the first measure of increasing PSA is noted in the series of 3. (40)
- 10.5 PSA Progression-Free Survival: Measured from date of randomization to date of PSA progression or death due to any cause.

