1.0 OBJECTIVES

- 1.1 The primary objective is to evaluate overall survival using adjuvant systemic therapy in high risk localized prostate cancer patients following radical prostatectomy. Disease-free survival will also be evaluated. Patients will be randomized to one of the following arms:
 - a. bicalutamide (Casodex[®]) + goserelin acetate (Zoladex[®])
 - b. mitoxantrone + prednisone administered with Casodex[®] + Zoladex[®].
- 1.2 To compare qualitative and quantitative toxicity between the two study arms.
- 1.3 To compare the two treatment arms with respect to PSA progression-free survival.
- 1.4 To test whether PSA progression is a surrogate endpoint for survival or disease-free survival in this clinical trial.
- 1.5 To evaluate promising biomarkers with respect to predicting PSA progression, disease-free survival, and overall survival.
- 1.6 To collect specimens (blood and prostatectomy blocks) for future biomarker (immunohistochemistry, proteomics, genomics) studies and correlations with outcomes.

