9.0 STUDY CALENDAR

9.1 Arm 1 Hormonal therapy alone

REQUIRED STUDIES	PRE	Mo	Ω						
	STUDY	1	4	7	10	13	16	19	22
PHYSICAL									
History and Physical Exam	X		X	X	X	X	X	X	X
Weight and Performance Status	X		X	X	X	X	X	X	X
Toxicity Notation		X	X	X	X	X	X	X	X
LABORATORY / TESTS									
PSA ¥	X		X	X	X	X	X	X	X
CBC/diff/platelets	X**								
Bilirubin	X**								
SGOT	X**								
Testosterone §	X			X		X		X	
Blood specimens π	X			X					
Tissue Specimen ™	X								
X-RAYS AND SCANS									
Bone Scan §	X								
CT/MRI abdomen and pelvis Σ	X								
OTHER X-RAYS/SCANS									
EKG	X								
MUGA or 2-d Echo	X*								
TREATMENT (Sect. 7.0)									
Radical Prostatectomy ∞	X								
Goserelin acetate (Zoladex®) #		X	X	X	X	X	X	X	X
Bicalutamide (Casodex®) √		X	X	X	X	X	X	X	X

NOTE: All forms to be used for this study are found in Section 18.0. Form submission guidelines are found in Section 14.0.

** Results of these tests do not determine eligibility but should be done prior to registration in accordance with good medical practice (see Section 7.1a). With the exception of blood counts, significant deviations in the values of these tests should be discussed with the Study Coordinator.

These tests are required during treatment as scheduled to assess toxicity.

π Blood specimens for patients opting to participate in the blood and tissue banking should be collected prestudy, between Weeks 24 and 28, and at progression (see Section 15.0).

Σ See Section 5.9. CT scan of abdomen and pelvis must be performed if patient has symptoms of distant metastatic disease.

Every 3 months.

√ Daily.

Ω Treatment and parameters will continue for a total of two years according to the schedule outlined above.

After off treatment, patients will be followed for disease status with Physical Exam and DRE (if PSA \geq 0.1 ng/ml), repeated at end of treatment and every six months for two years and annually thereafter for three additional years. All patients will be followed for 15 years or until death, and PSA will be collected as noted below.

* At prestudy, only for patients with underlying cardiac disease or CHF.

§ For patients with PSA \geq 20 ng/ml at diagnosis.

∞ Must be done within 120 days prior to registration.

™ For patients with adequate tissue and who consent to tissue banking (see Section 15.0 for details).

¥ Testosterone is collected every six months until it reaches the institutional lower limit of normal (ILLN).

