After off treatment, patients will be followed for disease status with Physical Exam and DRE (if PSA \geq 0.1 ng/ml), repeated at end of treatment and every six months for two years and annually thereafter for three additional years. All patients will be followed for 15 years or until death, and PSA will be collected as noted below.

* At prestudy, only for patients with underlying cardiac disease or CHF. Follow-up MUGA or 2-d echo is only needed for those patients who required one at baseline.

\ddagger For patients with PSA \geq 20 ng/ml at diagnosis.

∞ Must be done within 120 days prior to registration.

$^{\text{TM}}$ For patients with adequate tissue and who consent to tissue banking (see Section 15.0 for details).

\ddagger Testosterone is collected every six months until it reaches the institutional lower limit of normal (ILLN).

PSA is collected every three months for five years, and then every 6 months until 15 years or death.

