- 11.5 In addition to the study monitoring mentioned above, three formal interim analyses will be done. The decision to terminate accrual early will be made by the DSMC, and will consider disease-free survival, toxicities, and other factors in addition to survival. Additionally, the Southwest Oncology Group Statistical Center will closely monitor throughout the trial whether there is differential use of optional radiotherapy between the two treatment groups and this information will be provided to the DSMC at regular intervals.
- 11.6 The first formal interim analysis will be done after 700 patients have been entered, approximately 6 years after the study opens. Evidence suggesting early termination of the trial would be if the alternative hypothesis of a 30% improvement in survival with the MP + CZ combination arm is rejected at the 0.005 level, using an extension of the logrank test that allows for testing a relative risk not equal to 1. In addition, the null hypothesis of no difference in survival will be tested at the one-sided level of 0.005. The second interim analysis will be performed after 50% of the total expected deaths (275 deaths) will have occurred. Testing will be done as above at the 0.005 level. A third interim analysis will be performed 2.5 years after accrual has been completed. This testing will also be done at the alpha=0.005 level. The final analysis will be performed at the 0.045 significance level, approximately 4 years after accrual has been completed.
- 11.7 Secondary analyses will also be done regarding disease-free survival and toxicities. With 680 patients per arm, toxicity rates can be estimated to within at \pm 4% (95% confidence interval).

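### Section 10.4 counts progression without a PSA rise as PSA progression, which can bias the disease-free-survival half of objective 1.4 by an amount the documents do not allow us to size

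*Combined protocol and SAP*

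**What the plan says.** Objective 1.3 is "To compare the two treatment arms with respect to PSA progression-free survival". Objective 1.4 is "To test whether PSA progression is a surrogate endpoint for survival or disease-free survival in this clinical trial".

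Section 10.4 defines the marker in two limbs. The first is three consecutive PSA values above 0.2 ng/mL. The second applies when PSA is not rising: "in the absence of increasing PSA, a positive bone scan result or other radiographic or histologic evidence of progression will be used". One dating sentence follows: "Date of progression will be the date that the first measure of increasing PSA is noted in the series of 3". Section 10.5 builds PSA progression-free survival on this definition.

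Section 10.2 defines DFS as "Measured from date of randomization to date of first observation of recurrence or death due to any cause". It does not define recurrence and does not mention PSA.

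Section 11.7 says "Secondary analyses will also be done regarding disease-free survival and toxicities". Section 11 gives no method for objective 1.4.

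**The concern.** A surrogacy analysis needs a marker that is measured separately from the endpoint it is meant to stand for. A man whose disease recurs on a scan or biopsy while his PSA stays flat is a case where PSA failed to signal the outcome. Section 10.4 records him as having PSA progression. If the scan or biopsy finding is also his DFS event, the same finding enters both sides of the comparison, and a case against surrogacy is counted in its favour.

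What is at stake is the credibility of one half of a secondary objective. A PSA-DFS association reported under objective 1.4 could look stronger than PSA alone would justify, and a reader could not tell from the label PSA progression that some of the marker events were not PSA events.

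**Working it through.** There is no stated figure to reproduce. The check sets the definitions side by side, then asks when the overlap changes a result.

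**1. How each type of patient is classified** (clinical reading of recurrence in 10.2)

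| Course | 10.4 marker | PSA-only marker | DFS event |
|---|---|---|---|
| PSA rise, later clinical recurrence | yes, dated at first rising value | yes | yes, at recurrence |
| PSA rise, no recurrence | yes | yes | only at death |
| Clinical recurrence, no PSA rise | yes, no date rule in 10.4 | no | yes, at recurrence |
| Death with neither | no | no | yes, at death |

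Only the third row differs between the two markers.

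**2. Direction of the effect.** Let E be the DFS events that follow a PSA rise, k the recurrences without a PSA rise and D the deaths with neither. Let T1 and T0 be the person-time with the marker on and off.

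- PSA-only marker: rate ratio = (E/T1) / ((k + D)/T0).
- 10.4 composite, marker switched on the same day as the event: rate ratio = ((E + k)/T1) / (D/T0). Person-time does not change, because the patient leaves the risk set that day.
- Composite divided by PSA-only = (E + k)/E × (k + D)/D. This exceeds 1 whenever k > 0.
- Time-dependent marker that must precede the event: the k patients have their event while the marker is still off, so the ratio is the PSA-only one and the factor is 1.
- Landmark analysis in patients still event-free: a recurrence without a PSA rise before the landmark removes the patient, and one after it finds him marker-negative. The factor is again 1.

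So the definition permits inflation, and the unstated method decides whether it occurs.

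**3. Size.** The formula needs k, E and D, and the documents give none of them. They give 1,360 planned patients, a relapse risk of 40% or more with the type of relapse not stated (Section 2.0), and 275 deaths as half of those expected, so 2 × 275 = 550 (Section 11.6). None of these shows how many recurrences come without a PSA rise.

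The surveillance rules do not settle it either. The study calendars mark bone scan and CT/MRI at prestudy only, with the footnote "CT scan of abdomen and pelvis must be performed if patient has symptoms of distant metastatic disease", and the off-treatment rectal exam depends on PSA. That suggests k is small. The Fast Fact Sheet, labelled as a resource only, instead lists bone scan and CT every three months until progression. I therefore give no numerical range.

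**4. Dates.** The dating sentence in 10.4 fits only a PSA series, so it does not cover the second limb. The data do hold a date. The Treatment Form and the Chemotherapy Treatment Form ask about progression as defined in Section 10.0, and a yes requires the Follow-Up Form (64587), which records the date and site of relapse or progression. The gap is in the rule.

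**5. Delay if the marker starts at the third value.** From the first to the third value is two intervals: 2 × 3 months = 6 months in years 0 to 5, and 2 × 6 months = 12 months after that.

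**The case against.** The strongest reply is that the harm comes from a method the plan does not prescribe. A marker that switches on at the very event it should predict is poor analysis, and 10.4 does not call for it. This stands, and it is why no inflation factor is claimed. It does not remove the point: a label that mixes PSA and non-PSA events, with no stated method, leaves that analysis open.

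A second reply is that such events are probably few. The calendars support this and the Fast Fact Sheet does not, so the number stays unknown.

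A third is that 10.4 cites a published natural-history study, which may date the non-PSA limb. That cannot be checked from these documents, and the rule should be in the protocol in any case.

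A reader might infer more than the text supports:

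- *That DFS and PSA progression-free survival are the same endpoint, so the DFS half of 1.4 cannot be tested.* This would follow only if recurrence in 10.2 meant the 10.4 event. The objectives name DFS and PSA progression-free survival separately, and 10.2 and 10.5 define them separately. The Amendment 3 summary reports that 10.2 moved from progressive disease to recurrence, that 10.4 was retitled PSA Progression and that 10.5 was added. That separation favours the clinical reading.
- *That marker and endpoint share events by explicit rule.* Recurrence is undefined, so the overlap rests on its ordinary meaning.
- *That non-PSA events are undated in the data.* Form 64587 collects the date and site.

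**Conclusion.** The point holds in a limited form. On the clinical reading of recurrence, progression without a PSA rise enters both the marker and the endpoint in the DFS half of objective 1.4, and a recurrence that PSA missed is scored in favour of PSA. This can inflate a patient-level association and cannot be sized from the documents. A marker required to precede the event, or a landmark analysis, shows none.

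The conclusion rests on two assumptions: that imaging or histologic progression after prostatectomy is a recurrence under 10.2, and that the 10.4 definition would be used unchanged for objective 1.4. Overall survival, its power, the 11.6 tests and the survival half of 1.4 are not affected, because the 10.4 marker does not include death. The missing date rule and the undefined recurrence are clarifications and would not carry the point alone. The case for change is that a better marker is available at little cost.

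**What to change.** **Main change, in Section 11.7.** For objective 1.4, define a PSA-only marker: three consecutive values above 0.2 ng/mL, taken from the dated values on the PSA Reporting Form (59255). Analyse it by landmark, or as a time-dependent marker, among patients still free of a DFS event. A recurrence without a PSA rise then counts only as the DFS event. Switch the marker on at the third value, because status is not known earlier. Report the 10.4 composite and first-value dating as sensitivity analyses. The 10.4 definition can stay as it is for objective 1.3.

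**Clarifications.** In 10.4, date non-PSA events at the first positive scan or histology. In 10.2, state that recurrence means clinical recurrence. If PSA-only events are to be included, test surrogacy against overall survival only.

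**Cost.** A few sentences in three sections and no new assessments. The downsides are:

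- Marker status is delayed by about 6 or 12 months, depending on the PSA schedule.
- Recurrences between the first and third values count as marker-negative, which pulls the association down. The first-value analysis shows how much this matters.
- The form list for Expanded Participation Project (EPP) sites names no PSA form, so the availability of their PSA data must be checked.
- Form 64587 asks about a first relapse or progression, so a clinical recurrence after a reported PSA relapse may need a data query.

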11.0 STATISTICAL CONSIDERATIONS

- 11.1 The primary objective of this study is to compare the overall survival in prostate cancer patients treated with combined androgen blockade (LHRH agonist and anti-androgen) with that in patients treated with the combination of combined androgen blockade and mitoxantrone plus prednisone. Mitoxantrone, prednisone and combined androgen blockade would be judged superior to the standard regimen of combined androgen blockade if the true increase in median survival is 30%.
- 11.2 It was initially anticipated that 250 eligible patients per year would be accrued to this study. However, accrual has been slower than expected. Instead of the original accrual period estimate of 5.5 years, we now anticipate a period of 9.5 years in order to randomize 680 eligible patients per arm.
- 11.3 A median survival of 10 years is anticipated on combined androgen blockade. Assuming exponential survival, 9.5 years of patient accrual, and an additional 4 years of follow-up, a sample size of 680 patients per arm, this study has .92 power to detect a 30% increase in median survival, using a one-sided test with 0.05 significance level.
- 11.4 This study will be monitored throughout the accrual and follow-up periods by the Southwest Oncology Group Data and Safety Monitoring Committee (DSMC). The DSMC will be approved by CTEP and will include members both from within the Group and from outside the Group. A majority of the DSMC will be outside members, and at least one outside member will be a patient advocate and at least one will be a statistician. The

Group Statistician and two representatives of CTEP will be non-voting members. The Group Chair may not be on the DSMC. The DSMC will be provided with administrative reports every 6 months by the Study Statistician, and will discuss the reports if necessary at a meeting held in conjunction with the Southwest Oncology Group Meeting. The DSMC and study statistician will be the only individuals with regular access to the primary outcome data and this information will be provided to the DSMC on a regular basis.

- 11.5 In addition to the study monitoring mentioned above, three formal interim analyses will be done. The decision to terminate accrual early will be made by the DSMC, and will consider disease-free survival, toxicities, and other factors in addition to survival. Additionally, the Southwest Oncology Group Statistical Center will closely monitor throughout the trial whether there is differential use of optional radiotherapy between the two treatment groups and this information will be provided to the DSMC at regular intervals.
- 11.6 The first formal interim analysis will be done after 700 patients have been entered, approximately 6 years after the study opens. Evidence suggesting early termination of the trial would be if the alternative hypothesis of a 30% improvement in survival with the MP + CZ combination arm is rejected at the 0.005 level, using an extension of the logrank test that allows for testing a relative risk not equal to 1. In addition, the null hypothesis of no difference in survival will be tested at the one-sided level of 0.005. The second interim analysis will be performed after 50% of the total expected deaths (275 deaths) will have occurred. Testing will be done as above at the 0.005 level. A third interim analysis will be performed 2.5 years after accrual has been completed. This testing will also be done at the alpha=0.005 level. The final analysis will be performed at the 0.045 significance level, approximately 4 years after accrual has been completed.
- 11.7 Secondary analyses will also be done regarding disease-free survival and toxicities. With 680 patients per arm, toxicity rates can be estimated to within at \pm 4% (95% confidence interval).

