(24 hours a day, 7 days a week, excluding downtimes for maintenance)
or call [contact] (Mon-Fri, 6:30am-4:00pm Pacific Time, excluding holidays)

Southwest Oncology Group Registration Form

SWOG Study No.

S | 9 | 9 | 2 | 1

Registration Step

1

Assigned Treatment Arm

Activation Date: October 15, 1999

Last Amended Date: March 15, 2006

Adjuvant Androgen Deprivation Versus Mitoxantrone Plus Prednisone Plus Androgen Deprivation in Selected High Risk Prostate Cancer Patients Following Radical Prostatectomy, Phase III

Patient's Name _____

SWOG Patient ID

Other Group Patient ID

Other Group Name/
Protocol Number _____

INSTRUCTIONS: All of the information on this Registration Form and the Protocol Eligibility Section must be answered appropriately for a patient to be considered eligible for registration. This Registration Form must be entirely filled out and referred to during the registration. Do NOT submit this form as part of the patient data.

Caller's SWOG Roster ID

IRB Approval Date

/ /

Date Informed Consent Signed

/ /

SWOG Investigator Number

OR

Other Group Investigator Name and Number

/ _____

SWOG Treating Institution Number

OR

Other Group Treating Institution Name and Number

/ _____

Please indicate how the patient answered the following questions on the consent form:

1. My specimens may be kept for use in research to learn about, prevent, treat or cure cancer.

Yes No

2. My specimens may be kept for use in research about other health problems (for example: diabetes, Alzheimer's disease, or heart disease).

Yes No

3. Someone may contact me in the future to ask me to allow other uses of my specimens.

Yes No

Patient's Date of Birth: / /

Patient's Sex: Female Male

Method of Payment:

Patient's Ethnicity:

Patient's Race (select all that apply):

White or Caucasian Native Hawaiian or Other Pacific Islander American Indian or Alaska Native
 Black or African American Asian Unknown

If a U.S. resident:

Patient's Social Security Number: - -

Country of Residence, if not USA: _____

If a resident of Canada: Social Insurance Number: - - - - Postal Code: - -

Stratification Factors:

Height: cm

Weight: . kg

BSA: . m²

Performance Status:

Pathologic stage of disease: Organ confined Not organ confined, but N0 N1

Gleason's Sum: <7 7 >7 RT intended: Yes No

26636

3/15/2006

Southwest Oncology Group Registration Form Code Sheet

12/8/2004

Race code definitions:

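### Section 11 leaves the final survival test unnamed and uses no baseline covariates; pre-specified adjustment for age, performance status and the 6.1 factors could add a few points of power

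*Combined protocol and SAP*

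**What the plan says.** Section 10.1 defines overall survival, the primary endpoint: "Measured from date of randomization to date of death from any cause".

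Section 11.3 gives the design: "A median survival of 10 years is anticipated on combined androgen blockade", exponential survival, 680 patients per arm, 9.5 years of accrual and 4 further years of follow-up. It concludes that "this study has .92 power to detect a 30% increase in median survival, using a one-sided test with 0.05 significance level". It names no test statistic.

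Section 11.6 plans three interim analyses and a final one. For the interim test of the 30% alternative it specifies a statistic, "using an extension of the logrank test that allows for testing a relative risk not equal to 1". For the interim test of the null it gives a one-sided level of 0.005 and no statistic. For the end of the trial it says only: "The final analysis will be performed at the 0.045 significance level". No part of Section 11 mentions stratification or covariates.

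Section 6.1 balances the arms on pathologic stage, Gleason's sum and planned radiotherapy. Section 11 does not say that the analysis uses these factors. The registration form in Section 18.2 has fields for "Patient's Date of Birth" and performance status as well as the three balancing factors. It prints performance status under its stratification heading, but 6.1 does not list it. Section 5.0 sets no age limit, and 5.3 restricts performance status to 0 or 1.

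**The concern.** Over follow-up of 4 to 13.5 years, many deaths from any cause could be driven by age and general health and not by the assigned treatment. Where such factors are strongly prognostic, a proportional hazards analysis that ignores them estimates a treatment effect closer to the null than the effect among men of the same age and fitness. A model that includes them has more power for the same patients and deaths. Here the information is collected before allocation and is not used.

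The silence on the final test matters too. A test and covariate set not named in advance can be chosen after the data are seen.

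The January 2007 closure memorandum makes efficiency more valuable. It reports 488 patients registered to the chemotherapy arm, against 680 planned, and no more can be added.

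**Working it through.** **1. The plan's own figure.** Inputs from 11.3: medians 10 and 13 years (ratio 1.3, hazard ratio 1/1.3 = 0.769), accrual A = 9.5, follow-up F = 4, 680 per arm. With exponential survival and uniform accrual, and L = ln 2/median,

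P(death) = 1 − [exp(−L·F) − exp(−L·(A+F))]/(L·A).

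- Control, L = 0.0693: 1 − (0.7579 − 0.3923)/0.6585 = 0.445.
- Experimental, L = 0.0533: 1 − (0.8079 − 0.4868)/0.5065 = 0.366.
- Deaths: 680 × (0.445 + 0.366) = about 551. Half is 276, against 275 in 11.6.

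Schoenfeld power = Φ(√551 × ln 1.3/2 − z), where √551 × ln 1.3/2 = 3.08.

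- One-sided 0.05: Φ(3.08 − 1.645) = 0.924. Freedman's formula gives 0.922.
- One-sided 0.045: Φ(3.08 − 1.695) = 0.917.

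The .92 therefore reproduces with no covariate in the analysis. (The 0.045 is read as one-sided, as in 11.3; 11.6 does not repeat the sidedness.)

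**2. What adjustment adds.** The documents give no age distribution and no prognostic effects, so these are assumptions: age normal with SD 7 years, 15% of patients with performance status 1, and three strengths of effect. Other settings: 680 per arm, uniform accrual, exponential survival given the covariates, control median held at 10 years, one-sided 0.05. Cox tests of arm were run without covariates and with age and performance status.

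| Hazard ratio per 10 years of age; for PS 1 | Marginal HR 0.769: unadjusted, adjusted | Conditional HR 0.769: unadjusted, adjusted |
|---|---|---|
| 1.5; 1.3 | 0.921, 0.934 | 0.927, 0.935 |
| 2.0; 1.5 | 0.933, 0.953 | 0.903, 0.932 |
| 2.5; 2.0 | 0.929, 0.969 | 0.862, 0.927 |
| 1.0; 1.0 | not run | 0.923, 0.924 |

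(With no covariate effect, marginal and conditional ratios coincide.)

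The marginal column used 2,500 trials per row and the conditional column 1,500. The standard errors are about √(0.93 × 0.07/2500) = 0.5 point and √(0.90 × 0.10/1500) = 0.8 point per figure. Both tests were run on the same simulated trials.

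Gains are 1.3, 2.0 and 4.0 points in the marginal case and 0.8, 2.9 and 6.5 points in the conditional case. Under the null in the middle scenario both tests rejected 5.2% of the time at a nominal 5%.

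**3. Cross-check.** Dropping the covariates shrank the log hazard ratio by factors of about 0.969, 0.937 and 0.893.

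- Marginal ratio fixed, adjusted power = Φ(3.08/factor − 1.645): 0.938, 0.950, 0.964, against 0.924 unadjusted.
- Conditional ratio fixed, unadjusted power = Φ(3.08 × factor − 1.645): 0.910, 0.893, 0.866, against 0.924 adjusted.

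The sizes agree with the simulation to within about 2 points. In terms of events, 1/factor² = 1.065, 1.14 and 1.25, so adjustment is worth about 6%, 14% and 25% more deaths.

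The 6.1 factors were not in these simulations. Their contribution is not quantified.

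**The case against.** A reader might infer that the plan commits to an unadjusted logrank test as its primary analysis. The documents do not say so. The logrank wording belongs to the interim test of the alternative, and the null and final tests carry only a significance level. That an ordinary logrank test was meant is a fair guess, but still a guess.

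A reader might also infer that the trial falls short of its stated .92. Under the plan's assumptions it does not. The difference between 0.924 and 0.917 is the cost of testing at 0.045 and has nothing to do with age. The larger shortfalls in the conditional column arise only if 1/1.3 is taken as the effect among men of equal age and performance status. Section 11.3 instead describes exponential survival in each arm with a ratio of medians, which is a marginal statement. With the marginal ratio near 0.769, unadjusted power stays at 0.92 to 0.93 in all three scenarios.

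Three further points stand. An unadjusted test in a randomized trial is valid, and its error rate already allows for chance imbalance in age. The size of the gain rests wholly on assumed effects. Adjustment is not free: the hazard ratio is not collapsible, so the adjusted estimate is not the contrast of medians in 11.1 and 11.3, and the interim test of the 30% alternative has to be put on the same scale.

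None of this removes the narrower point. The final test is unspecified, usable baseline data are in hand, and adjustment kept the error rate and lost no power when the covariates had no effect.

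**Conclusion.** The point holds as an efficiency and pre-specification improvement. It is not an error in the sample size or a threat to validity. The expected gain is about 1 to 4 points of power if 0.769 is the marginal hazard ratio, about 1 to 6.5 points if it is the conditional one, and nil if age and performance status are not prognostic. These figures assume an age SD of 7 years, hazard ratios of 1.5 to 2.5 per decade of age and 1.3 to 2.0 for performance status 1, and the full planned accrual. Most of the gain is likely to come from age, because performance status has only two eligible levels. With fewer patients than planned, power sits on a steeper part of its curve, so the same relative gain in information would matter more. The control-arm count at closure is not given, so no figure is put on that here.

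**What to change.** In Section 11.6, name the primary test of overall survival as a Cox model test of arm, adjusted for age (continuous, from date of birth), performance status (0 v 1), pathologic stage, Gleason's sum and planned radiotherapy in their 6.1 categories. Keep the existing significance levels. State the functional form for age and the rule for missing covariates.

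Put the interim test of the 30% alternative on the same scale, saying whether 1.3 is meant as a marginal or a conditional ratio. The difference is modest: in the scenarios above, a marginal 0.769 corresponded to conditional ratios of about 0.763, 0.756 and 0.745.

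Keep the unadjusted logrank test and Kaplan-Meier estimates by arm as supportive, so that the contrast of medians in 11.1 and 11.3 is still reported. Fix the text before final data are seen. Because 11.4 gives the study statistician and the monitoring committee regular access to outcome data, someone without that access should write it.

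The cost is about a paragraph of text, with no new data, patients or follow-up. The real downside is that the primary hazard ratio becomes conditional on the covariates.
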